10.1 Ethical and other NHS Approvals

Approvals for this study will be sought from NHS Research Ethics Committee, Health Research Authority (HRA) and NHS R&D prior to commencement. The study will not be initiated before the protocol, Consent Forms and Participant Information Sheets have received approval/ favourable opinion from the REC. Should a protocol amendment be made that requires REC approval, the changes in the protocol will not be instituted until the amendment and revised informed Consent Forms and Participant Information Sheets (if appropriate) have been reviewed and received approval/ favourable opinion from the REC. A protocol amendment intended to eliminate an apparent immediate hazard to participants may be implemented immediately providing that the REC are notified as soon as possible and an approval is requested. Minor protocol amendments only for logistical or administrative changes may be implemented immediately; and the REC will be informed. Planned deviations from the protocol will not be permitted, any accidental deviations will be documented (to avoid recurrences) and reported to the Chief Investigator and sponsor immediately. All correspondence with the REC will be retained in the Study Master File.

[figure not shown]
The study will be conducted in accordance with the ethical principles based on the UK Policy Framework for Health and Social Care (Health Research Authority, 2017), Good Clinical Practice and the Declaration of Helsinki 1996 (Organization, 1996).

The sponsor and funder reserve the right to discontinue the study at any time for failure to meet expected recruitment goals, for safety or any other administrative reason. The sponsor and funder shall take advice from the Programme Steering Committee as appropriate in making the decision. There are no formal statistical criteria for stopping the study early.

10.2 Deception

Participants will be informed of all research activities prior to participating in the study thus there are no risks of deception.

During the interviews some topics of conversation around experiencing cognitive issues and accessing support services to help people with MS manage these cognitive problems may cause some discomfort or distress to the people with MS. Enough time will be given for debrief after the meeting. The interviewers will be actively looking for cues of distress or discomfort and they will check

with participants whether they wish to continue, and proceed only with their permission. If the participants no longer wish to continue and consent is withdrawn, one member of the research team will take them out of the room to allow debrief and to provide support, as needed.

Contact information on appropriate referral sources will also be provided for participants who feel they need further information/support with respect to cognitive problems in MS. If needed, people with MS will also be advised to approach their General Practitioner (GP). Also, the participants will receive the contact details of the research team in case of any enquiry about the research.

10.3 Consent

The process for obtaining participant informed consent will be in accordance with the REC guidance, and Good Clinical Practice (GCP) and any other regulatory requirements that might be introduced.

[figure not shown]
Ten participants identified as having mild cognitive problems will be invited to take part in an additional case study where they will receive the NEuRoMS intervention and will later be interviewed. A member of the clinical team will explain the case study to the participant at their routine clinical appointment. With the patients' permission, the Assistant Psychologist or Research Nurse will then contact them with a Participant Information Sheet and Consent Form. Participants will be asked to provide consent via Phone/Videoconferencing, online, or Post (see Section 7.4 for Informed Consent), or can bring signed copies of their Consent Form along to the session (if meeting face-to-face —dependent on Government and NHS advice). Patients and intervention providers will also be asked to provide their consent for the intervention sessions to be recorded for fidelity and supervision purposes.

Other stakeholders will either give consent for the interviews orally over the phone/videoconferencing, online, or complete hardcopies if preferred. Participants will receive a copy of the signed and dated Consent Form and the original will be retained in the Study records. A copy of the patient's Consent Form will also be retained in their medical notes.

The decision regarding participation in the study is entirely voluntary and participants will be encouraged to take their time making this decision. The Participant Information Sheet will emphasize that consent regarding study participation may be withdrawn at any time without penalty. The Information Sheet will also provide contact details should the participant want to ask any questions about the study. No study-specific interventions will be done before informed consent has been obtained.

10.4 Right to Withdraw

The decision regarding participation in the study is entirely voluntary. The investigator or their nominee shall emphasize to them that consent regarding study participation may be withdrawn at any time without penalty or affecting the quality or quantity of their future medical care, or loss of benefits to which the participant is otherwise entitled.

Participants will not be withdrawn from the study if they do not want to be audio recorded. A researcher record of oral consent and notes from the interview can be taken instead of an audio-recording should the participant prefer.

10.5 Confidentiality and Data Protection

The only identifiable information will be the names and contact details of the participants, which will be stored separately to the interview data. Each participant will be assigned a Participant ID Number by a member of the research team, for use on the interview transcripts and the electronic database. The research team will make a separate confidential record of the participant's name and Participant ID Number stored at the University of Nottingham, to permit identification of all participants enrolled in the study, in case additional follow-up is required.

[figure not shown]
The interviews will be audio-recorded using an encrypted, Trust approved, digital recorder and transcribed. A Trust approved external company or a University approved secure, web-based automated interface will be used for transcribing the interviews. A confidentiality agreement will be in place before transferring the interview data to the external company. The audio-recordings of intervention sessions and interviews will be treated as confidential documents and held securely in accordance with regulations at the University of Nottingham. Participants will be informed in the Participant Information Sheet that this agreement may be breached to report an incident to the appropriate persons if they reveal something of concern that may put themselves or anyone else at risk. Source documents shall be restricted to those personnel approved by the Chief Investigator and recorded as such in the study records. Source documents shall be filed at the investigator's site and may include but are not limited to, Consent Forms, interview transcriptions, audio-recordings and records. Only study staff shall have access to study documentation other than the regulatory requirements listed below. All source documents shall made be available at all times for review by the Chief Investigator, Sponsor's designee and inspection by relevant regulatory authorities.

All study staff and investigators will endeavour to protect the rights of the study's participants to privacy and informed consent, and will adhere to the Data Protection Act, 2018. We will only collect the minimum required information for the purposes of the study. This will be held securely, in a locked room, or locked cupboard or cabinet. Access to the information will be limited to the study staff and investigators and any relevant regulatory authorities (see above). Computer held data will be held securely and password protected. All data will be stored on a secure dedicated web server. Access will be restricted by user identifiers and passwords (encrypted using a one way encryption method).

Electronic data will be backed up every 24 hours to both local and remote media in encrypted format.

10.6 Vulnerable Groups

The only group which will be participating in the research can be considered vulnerable adults are the patient participants. We will be clear about the voluntary nature of their participation, and we will provide them with sufficient time to consider participation and to discuss with others before they

participate. They are free to withdraw at any time, without such withdrawal affecting their rights or future care. Since we will only include those who can communicate in English, we will not need to amend any of the study documentation for other groups (e.g., those with language difficulties, e.g., aphasia). The initial contact will be made by a member of the clinical team.

10.7 Confidentiality

Each participant will be assigned a unique Participant ID Number, for use on the interview transcripts and the electronic database (see section 10.5 for confidentiality and data protection).

The audio-recordings of intervention sessions and interviews, and intervention record forms will be treated as confidential documents. Source documents shall be restricted to those personnel approved by the Chief or local Investigator and recorded as such in the study records (see section 10.5 for confidentiality and data protection).

10.8 Indemnity

Insurance and indemnity for clinical study participants and study staff is covered within the NHS Indemnity Arrangements for clinical negligence claims in the NHS, issued under cover of HSG. There are no special compensation arrangements, but study participants may have recourse through the NHS complaints procedures.

10.9 Sponsor

[figure not shown]
Nottinghamshire Healthcare NHS Trust will act as the main Sponsor for this study. The Sponsor's Standard Operating Procedures (SOPs) will be used to govern the conduct of all aspects of the study. The Sponsor will ensure the study is run in accordance with their SOPs and auditing and monitoring plan will be developed in partnership with the sponsor. A self-audit checklist will be developed and completed regularly by each site to ensure adherence to the protocol and accurate and complete data collection. The study will be managed and co-ordinated from the Division of Psychiatry and Applied Psychology, School of Medicine, University of Nottingham.

11 Funding

This study is funded by the NIHR Programme Grants for Applied research (ref no. RP-PG-0218-20002) and was peer-review by an anonymous panel of experts.

12 Payment

An inconvenience voucher worth £20 will be offered to each patient and family member/carer who participated in the interviews as a thank you for their time.

Patients taking part in the NEuRoMS intervention sessions will also have their travel expenses covered for face-to-face sessions (dependent on Government and NHS advice).

13 Patient and Public Involvement

[figure not shown]
Our research team has excellent networks with people with MS and we have an extensive track record of conducting research studies in MS. We have developed this proposal in conjunction with an MS-PPI group.

Our PPI co-investigators ([name] and [name], who have MS) have been involved with every key stage of the research process and offered guidance for the project. Work Package 1 gathered the views of people with MS, carers and family, charity volunteers and clinicians on the proposed programme of NEuRoMS research via interviews and focus groups, which helped shape our pathway and logic model. We have also organized and held two PPI engagement events to discuss the NEuRoMS screening and management pathway and present our findings to date.

We have received some very useful and positive verbal feedback from people with MS which has helped shape our research strategy and design. We aim to work closely with the people with MS and their families/carers through our MS PPI group to ensure we produce useful findings that can facilitate the transferability of the screening and management pathway into practice a range of healthcare settings. Our patient partners ([name] and [name]) and our PPI group will continue to be involved with every key stage of the research process providing us with the real life experiences of living with MS, and what they feel is needed.

14 Dissemination

Findings will be published in scientific journals and disseminated to scientific audiences, people with MS (e.g., MS Life Conference), policy makers, healthcare networks, relevant organisations and stakeholders. A summary of the study findings will be made available through the NEuRoMS web page and newsletters.

15 Appendices

Cognitive Screening and Management Pathway in MS -logic model v4 23.10.2019

Situation

Cognitive problems: Major concern, affects ≈70% of people with MS (pwMS), adversely affects quality of life, increases health service use; subtle and difficult to identify until they become severe; ≈50% have mild-moderate cognitive problems. Cognition is often not a major concern in MS clinics, with the focus being the physical symptoms of MS I dentifying and treating cognitive problems before they become severe may improve quality of life and reduce psychological distress.

Cognitive rehabilitation:

Psychoeducation and teaching different cognitive strategies may be effective in helping people with MS to better manage and cope with cognitive problems.

NICE recommends Assessment and treatment of cognitive problems, but is not based on robust evidence.

Currently: There is no routine cognitive screening or cognitive rehabilitation for pwMS, mainly due to NHS time and staffing pressures, as well as a focus on the management of other more physical symptoms of MS. NICE guidelines also drive the focus of clinical care (e.g., monitoring of disease modifying treatments.

Goals

- 1. Identify, as part of routine care, people with MS with cognitive problems
- timely, cognitive rehabilitation for mild cognitive problems

Deliver appropriate.

Resources: Staff training and supervision for both cognitive screening ('administering' tests, understanding the results and knowledge of the different referral pathways - on the basis of mood and severity of cognitive problems, delivery of the rehabilitation) and rehabilitation package. Helpline to support pwMS to complete screening at home; online rehabilitation resources for pwMS during and after rehabilitation.

Inputs

Staff capacity: MS Neurology teams:

Specialist MS Nurses, Neurologists,

Neuropsychologists, Occupational

Therapists (OTs), Physiotherapists,

Healthcare professionals (HCPs) such as

Assistant Psychologists (AP), Healthcare

Researchers, Administrative support.

PwMS: Information provided with the

screening link to support completion of

screening tests at home and in clinic.

Commissioners, Community specialist

services such neurorehabilitation and

psychological services - as routinely

have an impact in the referral they

Volunteers: People with MS, family

types of referrals).

such as PALS.

screening for cognitive problems may

receive (e.g., number of referrals and the

members/carers, other voluntary services

Partners: PPI team, MS charities.

Technology: Online screening technology, PC tablets/mobile phones, Internet (home and clinic).

Facilities: NHS Neurology Clinics, access to hospital rooms (intervention delivery)

Outputs

Online, mobile phone and PC tablet cognitive screening technology developed

Ginical pathway to identify people with cognitive problems. Cognitive screening results will not be diagnostic, but will facilitate discussions between clinician and pwMS on the appropriate referral pathway.

Manualised Brief Cognitive Rehabilitation (psychoeducation and cognitive strategies) for HCPs (e.g., OTs, APs, nurses) to provide standardised support and advice to pwMS with mild-moderate cognitive problems that is appropriate and practical, utilising different modes of delivery (e.g., face-toface, online, individual or group-based) based on staff capacity and patient preference.

Referral pathway (based on severity of cognitive problems and NICE guidelines for cognitive problems and mood problems).

Training package for MS Services to screen and treat manage mild-moderate cognitive problems

Ginical and commissioning toolkits for NHS

Promotional material for MS charities on screening and treatment of cognitive problems, and patient information materials.

Who we reach: pwMS with cognitive problems, MS services, commissioners, charities, families and friends of pwMS.

For the pathway's success, we need active engagement

Mechanisms

PwMS: supported and motivated to actively engage with the screen and treat pathway; understand the value of cognitive screening and are informed about how the results will be used (and by whom). Moderating variables such as fatigue, mood and dexterity issues may affect completion of tests both at home and in clinic.

Carers, family/ friends volunteers: support pwMS in adhering to the intervention.

Clinicians: skilled and empowered to deliver, monitor, and evaluate pathway; and to support pwMS: understand the rationale behind and the value of routine screening and timely management of cognitive issues in MS and (especially neurologists) are able to effectively communicate this to their clinical teams and

Commissioners: recognise importance of problem; recommend in commissioning specifications that services embed the pathway.

Charities: promote importance of early detection and management of cognitive problems; campaign for and influence service provision.

Pathway*1: needs to be easily accessible, flexible (to take into account differences in referral pathways between clinics with specialist psychological services embedded within them, and those who do not; referrals based on mood and/or cognitive problems) relevant, outcomes focussed

*Pathway developed based on Person-Centred Approach

Implemented and evaluated based on Damschroder et al.'s (2009) Consolidated Framework for Implementation Research

Outcomes

Immediate

Longer-term

For pwMS: Routine cognitive screenin and brief cognitive rehabilitation in test sites

Empowering pwMS and involving them in decision making and self-

Increased access to care, treatment & support for cognitive problems

Increased knowledge about cognitive problems in MS

For services: Resources optimised to manage cognitive problems

Increased knowledge about cognitive problems in MS

Shift towards treating MS symptoms holistically

Better treatment decision

Clearer referral pathways to neuropsychology/ OT services for cognitive nrohlems

For services and pwMS: mproved management of cognitive problems

[figure not shown]
Timely referral of pwMS with cognitive problems: Early intervention may delay the emergence and impact of severe cognitive problems

Routinely delivered care, treatment and support for cognitive problems to improve pwMS' coping, quality of life, independence in activities of daily living

More efficient use of NHS resources

Drivers: NHS Digital, MS Society/JLA top 10 research priorities; MS Trust Forward View report; NHS Commissioning Excellence; NHS England's Commissioning Guidance for Rehabilitation (2016); Adult Social Care Outcomes Framework 2015/16; NHS Outcomes framework (2015/16); King's Fund Better Value in the NHS report.

External influences: Time, challenges in engaging people with MS with cognitive problems, resource-stretched NHS Services and funding limitations. Assumptions: Clinicians are adequately trained, prepared and supported to deliver the cognitive screening and management pathway. The pathway is acceptable and part of the routine care. People with MS and carers are willing to engage. MS Clinics are willing to provide the pathway. Screening technology works. Brief Neuropsychological Rehabilitation is effective for people with MS who have mild cognitive problems. NICE will update MS treatment recommendation. Adequate financial resources to deliver the pathway are available.

NEuRoMS WP2ii Qualitative Study: Patient-Participant Semi-structured interview Guide

Final Version 2.0, 29.06.2021

[Note: As per the methodology, the semi-structured interview is only a guide, and is necessarily an iterative process (i.e., it gets modified slightly after each interview, based on the information that participants provide).]

Screening

[figure not shown]
- Can you give me your general impressions of using the screening tool(s)?
- Was there anything you particularly liked?
- Was there anything you particularly disliked or found difficult?

Screening and management pathway

- What do you see as the main challenges to delivering our approach to monitoring and supporting your cognitive problems?
 - o What can be done to address these challenges?

NEuRoMS cognitive management programme

- How did you find the NEuRoMS programme sessions?
 - o What did you find helpful/unhelpful about the programme sessions?
- How did you find the NEuRoMS resource book?
 - o What did you find helpful/unhelpful about the resource book?
- How did you find the NEuRoMS online video resources?
 - o What did you find helpful/unhelpful about the online resources?
- What do you think about where the sessions were held?
- What do you think about the person who delivered the sessions?
 - o Knowledgeable?
 - O Clear and understandable?
 - o Empathetic? Helpful?
- How do you think we could improve the cognitive management programme in the future?
- Have you experienced any changes since taking part in this study?
 - o What are these changes?
 - o How do you make sense of these changes?
- Is there anything else you would like to tell me about?

NEuRoMS WP2ii Qualitative Study: Clinician/ Intervention Provider-Participant Semistructured interview Guide

Final Version 1.0: 16.01.2020

[Note: As per the methodology, the semi-structured interview is only a guide, and is necessarily an iterative process (i.e., it gets modified slightly after each interview, based on the information that participants provide).]

Demographics

[figure not shown]
Gather demographic information about the participant and their job role.

Screening and management pathway

- How did the screening and management pathway work in your service?
- How well did the screening and management pathway work with your systems?
- What were the main facilitators to integrating the screening and management pathway within your service?
- What were the main barriers to integrating the screening and management pathway within your service?
 - O What can be done about the barriers?

NEuRoMS cognitive management programme (only for intervention providers)

- Please can you tell me about your experiences of delivering NEuRoMS cognitive management programme?
 - o What went well?
 - O What were the difficulties and how did you overcome them?
 - o How did you find the training that you received?
 - o How did you find using the manual?
 - o How did you find the clinical supervision at site/ by the trial therapists?
 - o How did you find the monitoring of your practice during the research study?
- How did participants find the NEuRoMS cognitive management programme?
 - Were there any particular aspects which were good or bad?
 - o Did participants experience any changes/benefits from the cognitive management programme?
- How do you think the cognitive management programme could be improved in the future?

NEuRoMS WP2ii Qualitative Study: Family Member/ Carer -Participant Semi-structured interview Guide

Final Version 1.0: 16.01.2020

[Note: As per the methodology, the semi-structured interview is only a guide, and is necessarily an iterative process (i.e., it gets modified slightly after each interview, based on the information that participants provide).]

Demographics

 Gather demographic information about the participant and their relationship to the person they support.

Screening

- Can you give me your general impressions of how your family member/friend found using the screening tool(s)?
- Was there anything you think they particularly liked?
- Was there anything you think they particularly disliked or found difficult?
- Did you provide your family member/friend with any support to complete the screening tasks?
- Were you surprised to hear that your family member/friend might have cognitive problems?

Screening and management pathway

- What do you see as the main challenges to delivering our approach to monitoring and supporting cognitive problems in MS?
 - o What can be done to address these challenges?

NEuRoMS cognitive management programme

- How do you think your family member/ friend found the NEuRoMS programme sessions?
 - What do you think they found helpful/unhelpful about the programme sessions?
- What do you think about where the sessions were held?
- What do you think about the person who delivered the sessions?
 - o Knowledgeable?
 - o Clear and understandable?
 - Empathetic? Helpful?
- How do you think we could improve the NEuRoMS cognitive management programme in the future?
- Has your family member/friend experienced any changes since taking part in this study?
 - o What are these changes?
 - o How do you make sense of these changes?
- Is there anything else you would like to tell me about?

16 References

- Chiaravalloti, N. D., & DeLuca, J. (2008). Cognitive impairment in multiple sclerosis. *The Lancet Neurology*, 7(12), 1139-1151. Retrieved from http://dx.doi.org/10.1016/S1474-4422(08)70259-X. doi:10.1016/S1474-4422(08)70259-X

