[name] [name] (Clinical Psycholgoy), [name] (Consultant Neurologist), [name] (Healthcare Research), [name] (Primary Care research), [name] (Health Services Managemnt), [name] (Healthy Psychology), [name] (Applied Health Services Research), [name] (Mental Health and Technology Research), [name] (Rehabilitation Psychology), [name] (Mental Health and Technology Research), [name] (Rehabilitation Psychology), [name] (Neuropsychology).

Swansea University

[name] (Health Economics)

[name] (Health Informatics)

PPI

[name]

[name]

NWORTH NWORTH CTU - North Wales Organisation for Randomised Trials in Health/ Bangor University

[name] (Statistician)

[name] (Statistician)

Please visit the NEuRoMS website for more information on the expertise of each research team member: https://neuroms.org/team/our-team

Clinical Team (from three multiple sclerosis (MS) clinics):

Neurologists, MS nurses, administrative staff, physiotherapists, occupational therapists, Clinical Research Network (CRN).

Assistant Psychologists and Research Nurses: Employed by participating NHS Trust or University of Nottingham, undertaking research and/or clinical activities specifically for NEuRoMS (including providing the NEuRoMS intervention).

2 Study Summary

Full Study Title	Neuropsychological Evaluation and Rehabilitation in Multiple
	Sclerosis (NEuRoMS): Refining the screen and management
	pathway in routine clinical practice (Phase 1: Work Package 2ii)
Short Study Title	Refining the neuropsychological screening and management
	pathway in routine clinical practice - Qualitative Study
IRAS ID	276903

Study Design Study Participants	10 case studies of people with multiple sclerosis (MS) who received the screening and NEuRoMS intervention, using routinely collected clinical notes and interviews with people with MS, staff who deliver the intervention/pathway, and carers or family members who support people with MS. People with multiple sclerosis, carers or family members, and
	clinicians delivering the screen and management pathway.
Study Sample Size	Qualitative study:
	People with MS: n=10
	Carers/ family members: n=10
	Clinicians: n=12 (4 clinicians from each site)
	Intervention providers: n=3 (One Assistant Psychologist or
	Research Nurse from each site)
Study Locations	Three MS clinics who delivered the screening and management
	pathway:
	 Nottingham University Hospitals NHS Trust Cardiff and Vale University Health Board

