screening profile and individual needs, but will focus on: psychoeducation, internal and external compensatory strategies; environmental modifications; and the importance of dealing with low mood and fatigue. Ten people with mild cognitive problems (3-4 from each site) will receive the NEuRoMS intervention and later take part in a semi-structured interview as part of 10 case studies. Qualitative analysis of the case studies will be reported to understand participants' experiences and identify any barriers/ facilitators to delivery of the screening and management pathway. The others will receive the NEuRoMS intervention following their next clinic appointment, when the intervention will be more established at each site.

We are interested in those with 'mild' cognitive problems in study, because the feedback we received from participants who took part in our previous cognitive rehabilitation trial (CRAMMS (Lincoln et al., 2019)) was that they had too severe cognitive problems to actually benefit from the rehabilitation. Participants felt that had they received the rehabilitation earlier, when their cognitive problems were milder, they may have been able to benefit more.

Research focus

The present study will investigate what potential benefits and issues people with MS who undergo neuropsychological screening encounter, and tries to identify any barriers/ facilitators to delivery of the screening and management pathway. Ten patients who experienced the neuropsychological screening (IRAS ID: 276570) and were identified as having mild cognitive problems, will be offered a manualized NEuRoMS intervention led by an Assistant Psychologist or Research Nurse. After completing the intervention, semi-structured interviews will be conducted with participants and related informants (family or carers) and clinicians to understand their experiences of the screening and management pathway. These qualitative case studies will help refine the pathway and facilitate its implementation.

5 Study Objectives

[figure not shown]
Primary Objectives and Outcomes

- To improve understanding of how the NEuRoMS screening and management pathway is integrated within routine clinical practice.
- To improve understanding of how the NEuRoMs intervention programme is experienced by those who deliver and receive it.

Secondary Objectives

- Refine intervention resource book and staff training package.
- Develop fidelity tools for the definitive trial.

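### The pathway section of the patient and family/carer interview guides asks only for challenges, so the results discussion, triage and the pathway as a whole get no positive prompt from 20 of 35 planned interviewees

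*Protocol*

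**What the plan says.** Section 4 (Research focus) makes the aim two-sided: the study "tries to identify any barriers/ facilitators to delivery of the screening and management pathway". Section 5 lists two primary objectives: how the pathway is integrated into routine practice, and how the intervention is experienced by those who give and receive it.

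Section 15 holds three interview guides, each with a section on the screening and management pathway.

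- **Patient guide.** One main question, "What do you see as the main challenges to delivering our approach to monitoring and supporting your cognitive problems", and a probe on how to address the challenges.
- **Family/carer guide.** The same question and probe, referring to cognitive problems in MS generally. Its screening section also asks: "Were you surprised to hear that your family member/friend might have cognitive problems".
- **Clinician/intervention provider guide.** It asks how the pathway worked and how well it fitted local systems, then "What were the main facilitators to integrating the screening and management pathway within your service", then the matching question on barriers. It uses the pathway's neutral name throughout that section.

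Each guide carries a note that it is only a guide and is modified slightly after each interview in light of what participants say. Section 6.2 states that a member of the research team does the interviews, that the research team designed the intervention, and that the guides were developed with the PPI co-investigators.

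**The concern.** An interview guide should be able to yield both halves of what the study sets out to find. Patients and informants go through parts of the pathway that are neither the screening tool nor the sessions: the discussion of results with a clinician, the decision on where the patient goes next, and how the steps join up. For these, the only specific pathway question they get asks what is difficult. If their interviews contain little on what helped at those steps, the analyst cannot tell whether nothing helped or nobody asked. Section 8.1 uses the themes to develop the pathway for later parts of the programme, so a feature worth keeping could be missed.

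Two wording points go with this. The word 'our', spoken by a member of the team that designed the intervention, is not neutral. The question on surprise is closed and names a single reaction, although section 6.3 seeks informants who live alongside or support the patient and who may have noticed problems already.

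**Working it through.** No sample-size or power formula applies. The check is a count of interviewees and a reading of every question in the three guides.

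**Step 1: planned interviewees (section 2, repeated in section 8.2).** "People with MS: n=10"; "Carers/ family members: n=10"; "Clinicians: n=12 (4 clinicians from each site"; "Intervention providers: n=3".

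- Clinicians: 4 × 3 sites = 12, as stated. Providers: 1 × 3 sites = 3, as stated.
- Total: 10 + 10 + 12 + 3 = 35. The protocol gives no grand total.

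**Step 2: which parts of the pathway get a positive prompt.** Section 6.3 (Clinicians) names three elements: screening, triaging and intervention. Set against the guides:

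| Part of the pathway | Patient guide | Family/carer guide | Staff guide |
|---|---|---|---|
| Screening tool | liked, and disliked or difficult | the same, about the relative or friend | within the general pathway questions |
| Results discussion and triage/referral | no specific question | no positive prompt; closed question on surprise at the outcome | within the general pathway questions |
| Intervention | helpful/unhelpful for sessions, resource book and videos | helpful/unhelpful for sessions | what went well and what was difficult (providers only) |
| Pathway as a whole | challenges only | challenges only | facilitators and barriers |

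The remaining items in the patient and family/carer guides (venue, the person delivering sessions, improving the programme, changes noticed, anything else to add) concern the programme or are general. None asks what worked in the results discussion, triage or the overall pathway.

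**Step 3: size.**

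- No positive prompt on those parts: (10 + 10) / 35 = 20/35 = 57%.
- Asked about both facilitators and barriers of the pathway: (12 + 3) / 35 = 15/35 = 43%.
- Asked the closed question on surprise: 10/35 = 29%, informants only.
- Asked paired positive and negative questions on screening tool and sessions: 20 of the 20 patients and informants.

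**The case against.** The strongest reply is that two of the three pathway elements already have balanced questions for all 20 patients and informants, and that what people liked in the screen or found helpful in the sessions is facilitator material. This stands, and it limits the point to the results discussion, triage and the pathway as a whole.

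It can also be said that patients and carers are poorly placed to judge integration within a service, so guides should differ by group. That justifies different wording. It does not explain why they are asked about challenges to delivery and not about what helped. The monthly teleconferences (section 6.2) do explore what works well, but only with clinicians.

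The note on iteration and the PPI input are real mitigations. However, changes are slight and follow what participants volunteer, so nothing ensures that an unasked topic is added.

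Four stronger readings are tempting, and the protocol does not support them:

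- *Facilitators are not elicited from patients and informants at all.* The paired questions on the screen and sessions show otherwise.
- *Answers are steered.* This is a possible risk only. Asking for challenges invites criticism while 'our' may inhibit it, so no net direction follows. The question on surprise can be answered no.
- *A comparison between groups is distorted.* Section 8.1 maps interviews to resources, context, mechanisms and outcomes. It plans no explicit comparison of facilitators between patients and staff.
- *A screening result is disclosed to a third party.* The patient chooses the informant and passes on the study documents (sections 6.3 and 6.4), and the item says only that there might be problems.

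**Conclusion.** The point holds in a narrow form and is minor. The aim covers barriers and facilitators, but for the parts of the pathway between and around the screen and the sessions, 20 of 35 planned interviewees (57%) are prompted only for barriers. The closed question on surprise is a separate wording weakness that reaches 10 of 35 (29%).

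These are counts of planned interviews by guide. They are not estimates of missing data or bias, and they assume full recruitment (including one informant per patient) and guides used as printed. How much material would be lost cannot be worked out from the protocol. No statistical figure in the plan is affected.

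**What to change.** Reword three lines in section 15.

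1. **Patient guide, pathway section.** Replace the question with a neutral pair that names the screening and management pathway, as the staff guide does, in place of 'our approach': what helped or worked well, and what got in the way, in how your cognition was checked, discussed and followed up? The probe on addressing difficulties can stay.
2. **Family/carer guide, pathway section.** Make the same change, worded for the person they support.
3. **Family/carer guide, screening section.** Replace the question on surprise with an open one: what, if anything, had you noticed beforehand, and how did you see the outcome of the screening?

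Sample, timetable and analysis are unchanged. Because the guides are appended to the protocol, the sponsor should check whether the REC must be notified under section 10.1. That is the only cost beyond the rewording.
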